Amisulpride. Amisulpride (4-amino-N-[(1-ethylpyrrolidin-2-yl)methyl]-5-ethylsulfonyl-2-methoxy-benzamide has a bioavailability of 48% and a half-life of about 12 hours (Rosenzweig et al., 2002). It binds selectively (<https://pubchem.ncbi.nlm.nih.gov/compound/2159>) to DA D(2) and D(3) receptors in the limbic system. It reaches its peak plasma levels after 1 hour and has a second peak after 3 hours. Amisulpride does not have active metabolites (Bergemann et al., 2005). Low doses of amisulpride block presynaptic D(2)/D(3)-dopamine autoreceptors, thereby enhancing dopaminergic transmission, whereas higher doses block post-synaptic receptors, thus inhibiting DA activity (Leucht et al., 2002). In this application, we will apply a high dose to take advantage of the DA D2 receptor blocking effects of amisulpride. We are orienting our dosing on previous research using a single dose of 400mg amisulpride to block post-synaptic DA D2 receptors during fMRI (Kahnt and Tobler, 2017). That dosage showed good tolerability (Rosenzweig et al., 2002). Whether this dose is tolerable in an AN population has not been established and is a goal of this study. Establishing pharmacokinetics with plasma levels will also be important but will be part of future larger studies.

Bromocriptine. Bromocriptine is a semisynthetic, ergot alkaloid with anti-Parkinson and lactation inhibitory activities. Bromocriptine selectively binds to and activates postsynaptic DA D2-like receptors in the central nervous system (CNS), its half-life is between 2 and 8 hours, and it does not have active metabolites (<https://pubchem.ncbi.nlm.nih.gov/compound/31101>). Bromocriptine has a bioavailability of 28% and reaches its peak plasma level around 3 hours after ingestion (Holt et al., 2010). Bromocriptine has been used in fMRI previously and modulated reward and reversal learning (Cools et al., 2009). Effects of DA synthesis capacity will be tested in future larger studies. We will apply a single dose of 1.25mg bromocriptine, which was effective in manipulating both fMRI and behavior results (Cools et al., 2009; Lissek et al., 2018).

Special Pharmacological Considerations. Bromocriptine is an anti-Parkinson medication available in the US. An investigational new drug (IND) application to the Federal Drug Administration (FDA) has been approved, IND # 141908. Amisulpride is an antipsychotic not freely available in the US; however, it can be purchased via Sanofi France as in previous studies (Admon et al., 2017). We have received an IND from the FDA, which allows for legal import of amisulpride. Both medications have a plasma peak of 3 hours, and fMRI will begin for all sessions at that time point after taking active drug or placebo. The half-lives for amisulpride of 12 hours, and 2-8 hours for bromocriptine are short enough to allow 3 days in between studies to suffice the 5 half-lives

rule for medication elimination from the body (neither medication has active metabolites) (Bergemann et al., 2005; Holt et al., 2010; Schatzberg and Nemeroff, 2013).

Handling of Study Medication

Storage Location: UC San Diego Health Eating Disorders Center for Treatment and Research, [name] (PI Office, [name])

Medications will be stored in a locked cabinet in the research office of the PI. That office is embedded in the UC San Diego Health Eating Disorders Research Program office suite, which is locked. Each study drug will be labeled with the statement “Caution: New Drug—Limited by Federal (or United States) law to investigational use.” (§312.6 Labeling of an investigational new drug.).

A randomization protocol will be developed ahead of the study using Research Randomizer (<https://www.randomizer.org>). The PI will randomize the study days for the three medications. A master file with the randomization of medication per subject will be kept by the study monitor ([name]).

While the tablets look slightly different, subjects will not be told what type of medication they receive on either day. Study participants have been drug naïve to any of the study medications, and we do not expect recognition. It is uncertain what specific effects each medication will have on brain function and there will therefore be no implicit bias.

Each subject will complete three MRI scan days (Study Visit 1, Study Visit 2, and Study Visit 3). On each day, the subject will consume one of the three medications (amisulpride, bromocriptine or placebo). Each subject will complete a baseline scan (P-fMRI), Amisulpride scan (A-fMRI), and Bromocriptine scan (B-fMRI) spaced 3 days apart (2 to 4 day acceptable range). This randomized study has 6 medication study arms listed below:

On the morning of each study day, the PI or other study staff not running the fMRI scanning procedures will provide the study subjects the medication as per randomization. Other study personnel that will run the fMRI scanning procedures will be kept blinded from the applied medication. This will help reduce bias by the study personnel.

There are no rater applied assessments on the study days so there is no rater bias based on the personnel end. The fMRI data are objective and thus unbiased.

The investigator will not supply the investigational drug to any person not authorized under this part to receive it. (§312.61 Control of the investigational drug.)

Neither study drug is a controlled substance. Nevertheless, the study medication packages with the investigational drugs will be in a securely locked, substantially constructed cabinet, in the PI’s office, which is within an office suite that is locked and accessible only to the research personnel.

Should the subject have a serious adverse reaction that required emergency treatment, the PI would be contacted and the blinding of the medication order would be broken in order to allow adequate treatment of the patient by emergency department staff.

Each subject will be randomized to one of the following groups:

1.

Scan 1: P-fMRI
Scan 2: A-fMRI
Scan 3: B-fMRI

2.

Scan 1: P-fMRI
Scan 2: B-fMRI
Scan 3: A-fMRI

3.

Scan 1: A-fMRI
Scan 2: P-fMRI
Scan 3: B-fMRI

4.

Scan 1: A-fMRI
Scan 2: B-fMRI
Scan 3: P-fMRI

5.

Scan 1: B-fMRI
Scan 2: P-fMRI
Scan 3: A-fMRI

6.

Scan 1: B-fMRI
Scan 2: A-fMRI
Scan 3: P-fMRI

Medication dosage

Amisulpride – Single Dose 400 mg and scan 3 hours post ingestion

Bromocriptine – Single Dose 1.25 mg and scan 3 hours post ingestion

Amisulpride

Contraindications: Amisulpride's use is contraindicated in the following disease states: Pheochromocytoma, concomitant prolactin-dependent tumors (e.g. breast cancer), movement disorders (e.g. Parkinson's Disease) and lactation. Subjects will be screened during the interview with the PI to ensure they do not have any of these conditions that are contraindicated.

Potential side effects during ongoing use include fever, excessive sweating, change in heart rate, chest pain, swelling, pain, and redness in the legs, increased frequency of infections, skin allergy, seizures, restless legs, twitches in the tongue and face, trembling, excessive salivation, constipation, decreased libido, weight gain, amenorrhea, gynecomastia, agitation and anxiety, tardive dyskinesia and neuroleptic malignant syndrome.

However, we will only include drug naïve individuals and the one-time application has been well tolerated in previous studies and we do not expect problems other than maybe nausea, which will be discussed as part of the IRB consent process (Rosenzweig et al., 2002).

Amisulpride has been used in similar ways in brain imaging research.

We expect to see if at all some nausea. The other side effects are in the context of prolonged prescription and not after single dose.

Subject Stopping criteria:

If a subject were to feel so nauseous she cannot perform the study it will be stopped. If there are any other symptoms that interferes with subjects' normal functioning we will stop the study.

Bromocriptine

Contraindications: This medication is contraindicated in syncopal migraines, uncontrolled hypertension, pheochromocytoma, prolactinoma, breast cancer, hypersensitivity/allergy to bromocriptine. Participants with a history of long QT syndrome or family history of sudden death or long QT syndrome will be exclusion criteria. A history of seizures or seizure disorder is an exclusion criterion. Subjects will be screened during the interview with the PI to ensure they do not have any of these conditions that are contraindicated.

Bromocriptine is a dopamine D2 receptor agonist for the treatment of Parkinson's Disease and Type 2 Diabetes.

The medication's potential common side effects for ongoing use as per the manufacturer include nausea, headache, stomach upset, dizziness, drowsiness, feeling faint, fainting, suddenly falling asleep. Serious side effects can include heart attack, stroke, pulmonary fibrosis.

Individuals who ever took the medication before will be excluded, and the one-time application should at most be associated with nausea, headache or dizziness (Diederer et al., 2017). For each study participant only a one-time application is planned, just prior to brain imaging. The objective is to enhance dopamine transmission in the brain. We will only include drug naïve individuals and the one-time application has been well tolerated in previous studies and we do not expect problems other than maybe nausea, which will be discussed as part of the IRB consent process.

Bromocriptine has been used in similar ways in brain imaging research.

Subject Stopping criteria: If a subject were to feel so nauseous or dizzy that she cannot perform the study it will be stopped. If there are any other symptoms that interferes with subjects' normal functioning we will stop the study.

Study Duration

Altogether, assessments will take about 3 hours, the Pre-Scan blood draw and EKG will take about an hour and each brain imaging session including breakfast, medication administration and pre-scan questionnaires will take about 4 hours. Total study duration therefore is about 16 hours.

Clinical Procedures and Interventions: Not applicable, all procedures are research related, no standard of care procedures or treatment provided.

Drugs & Devices

Administration of Drugs: The drugs amisulpride (400 mg) and bromocriptine (1.25 mg) will be administered in study, 3 hours prior to the MRI scan. Both drugs are investigational drugs and the PI, [name], has submitted and received approval from the FDA for this study (IND # 141908, see attached approval letter)

Associated Devices:

- MRI scans will be performed on a GE Discovery MR 750 3.0 T Scanner (see attached 510(k) FDA approval document (**Discovery MR750 FDA Approval - K142361.pdf**))
- EKG will be performed at the Altman Clinical Trials Research Institute.

Research Facilities and Research Procedures Performed at Facility

1. **UC San Diego Health Eating Disorders Center for Treatment and Research:** PI/Research Staff offices, subject recruitment, data storage, data analysis, consent visits, storage of medication.
2. **Altman Clinical Trials Research Center (ACTRI):** Pre-Scan Visit (blood draw and EKG, primary option).
3. **Center for Advanced Laboratory Medicine (CALM):** Blood test processing (serum pregnancy test, BUN, Creatinine, Electrolytes).
4. **Sharp and Children's MRI Center:** Study Visit 1, Study Visit 2, Study Visit 3
5. Medical Care San Diego: Pre-Scan Visit (blood draw and EKG, secondary option from ACTRI)
6. LabCorp: Pre Scan Visit (blood draw, secondary option from ACTRI)

Inclusion of Women and Minorities

Inclusion of Women: This project will study females with anorexia nervosa (AN) and healthy controls (HC). This project will study women only. Anorexia nervosa among males is relatively rare, males with AN have many atypical features (Andersen and Holman, 1997). Especially for a study design to be developed as in this application, it is important to keep variance, including sex, low. However, males will be included in future studies.

Inclusion of Minorities: The racial distribution of study participants with anorexia nervosa depends on individuals referred to the two treatment centers where we recruit from (UC San Diego Health Eating Disorders Center for Treatment and Research). Healthy controls will be matched to those individuals. The referral area to those treatment programs is primarily Southern California, however, the programs also draw patients nationwide. Therefore, it is reasonable to estimate subject recruitment based on the California State Census. As per the 2010 US Census data (factfinder.census.gov) the racial distribution of the population is as follows: White 57.6%, Black or African American 6.2%, American Indian/Alaskan 1.0%, Asian 13.0%, Native Hawaiian 0.4%, More than one race 4.9%; Non-Hispanic White 40.1%, Latino 37.6%. Number of subjects to be recruited is reflected in the Enrollment Table.

Minority groups present less often to treatment facilities. This may reduce access to individuals from a minority background. However, a special effort will be made for the recruitment of minority populations:

Study Population.

Eating disorders commonly occur in industrialized nations, but immigrants from nations where the disorders are rare assimilate and also may develop eating disorders, presumably because of exposure to thin-body ideals (American Psychiatric Association, 2000). There is very limited research on the prevalence of eating disorders in minority groups. However, anorexia nervosa was found to be more common in white compared to black individuals in one study (Striegel-Moore et al., 2003), and another found eating disturbances compared to Caucasian females to be equally common among Hispanic females, more frequent among Native Americans, and less frequent among Black and Asian American females (Crago et al., 1996). This highlights the need to reach out toward minority groups, in particular, Hispanic and Native American individuals. The nature of the study with many questionnaires and the specific neuroimaging tasks prohibit us to have all material and tasks in Spanish. However, it is our experience that the largest portion of individuals who might qualify for the study will be able to communicate in English. The applicant will approach those groups by providing teaching about eating disorders in those communities and provide information on the severity of illness and treatment options.

Outreach Plan.

We will make a special effort to match subjects with anorexia nervosa with healthy controls that come from similar ethnic background. There are several Universities in the San Diego area including UCSD as well as San Diego State University with multicultural student organizations.

We will carefully assess recruitment resources, incentives, and problem-solving mechanisms, and monitor the success closely.

Communication.

A main obstacle in the recruitment of minority groups is a lack of trust and knowledge (Outreach Notebook, NIMH). Thus, we will offer any of the contacted interested organizations to give a presentation regarding the study to promote understanding, awareness, and trust. The PI is already giving seminars to parents of patients with eating disorders or at local health fair events and will be more than happy to provide findings further and teaching for research staff, health care providers, participants, and their families and communities. This will increase trust and fruitful long-term collaboration.

Data Storage and Data Analysis Plan

All paper data will be stored in locked cabinets in the PI office space at UC San Diego Health Eating Disorders Center for Treatment and Research ([name]). All electronic data will be stored on the VRD server created for [name] lab by the ACTRI (see section 16 PRIVACY AND CONFIDENTIALITY CONSIDERATIONS INCLUDING DATA ACCESS AND MANAGEMENT below for more details).

We will extract for both tasks mean parameter estimates from 18 predefined anatomical regions of interest (ROIs) (<http://marsbar.sourceforge.net/>), automated anatomical labeling Atlas, AAL (Tzourio-Mazoyer et al., 2002) based on previous studies (DeGuzman et al., 2017): dorsal and ventral anterior insula, caudate head, gyrus rectus, medial, middle and inferior OFC, ventral striatum (O'Doherty et al., 2004) and nucleus accumbens (Breiter et al., 1997). Extracted ROI data will be analyzed using SPSS 24 (IBM statistical software) using repeated measures ANCOVA. Extracted regional brain activation parameter estimates will be tested for normality with the Shapiro-Wilk test, rank-transformed when non-normally distributed and analyzed using repeated measures ANCOVA with covariates as in previous studies to account for confounding factors such as comorbidity or medication (DeGuzman et al., 2017). Spearman's rank will be used for correlation analyses and controlled for multiple comparisons using bootstrapping (1000 samples) (Westfall, 2011). We will also conduct exploratory whole-brain analyses to test for areas of interest outside of our predefined ROIs and create PE response maps, with maps thresholded at voxel level $p < 0.05$, FWE corrected (very stringent), 10 voxel minimum cluster contiguity, as well as voxel level $p < 0.001$ and $p < 0.05$ cluster level corrected (exploratory),

Statistical Power. This is a developmental grant application and we cannot be certain whether the study has sufficient power. However, previous studies using comparable designs and similar sample sizes showed significant within and between group results (Diederer et al., 2017). Studies from our group (Frank et al., 2018a) indicated that subject groups of 20 per group should provide sufficient power based on for instance caudate nucleus PE parameter estimate means of 67.8 (adolescent AN) and 40.2 (adolescent controls), with a mean standard deviation of 28, to reach a power of 0.8, $p<0.05$. Thus, our sample size for the fMRI study should be adequate and be able to replicate our previous results (elevated PE) and provide adequate pilot data for the new analyses in this application. A main goal of this application to investigated data distribution, standard deviation, etc. for future studies.

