Alternatively, subjects may complete the Electrocardiogram (EKG) at Medical Care San Diego ([name]) and the labs (Creatinine, BUN, electrolytes and serum pregnancy test) at either the Medical Care San Diego ([name]) or a LabCorp location close to where the subject resides. Subjects who use these facilities to complete the EKG and labs will provide the PI and his staff with the test results. Subjects will need to complete these tests no more than one week prior to the first scheduled MRI scan. The research study will pay these facilities directly on the subject's behalf with the self-pay option. Once the PI receives the test results, if he feels the results are out of range he may withdraw the subject from the study.

Study Visit 1

Location: Sharp and Children's MRI Center ([name])

The morning of the imaging procedures the subject will go to the Sharp and Children's MRI Center for the scanning procedures. The medication will need to be administered 3 hours before the start of the scan.

When the subject arrives at the MRI Center, subjects will complete a urine pregnancy test. After the pregnancy test (test must be negative), the research assistant will take the subject's blood pressure and measure her heart rate and administer the study medication. The subject will complete the Taste Labeled Magnitude Scale, Hedonic Taste Preference Scale, Food Cravings Questionnaire (State), Eating Disorders Examination (EDE-Q), Temporal Experience of Pleasure Scale (TEPS), Eating Expectancy Inventory (EEI), Beck Depression Inventory (BDI-II), The Positive and Negative Affect Schedule (PANAS), and eat a standardized breakfast.

The research staff will then review study procedures and fMRI tasks.

Subjects will then complete the fMRI and structural MRI (details of tasks outlined below).

After the scan, the research assistant will take the subject's blood pressure and heart rate and will have the subject complete the Post Scan Pleasantness Ratings and the Post MRI Questionnaire.

The total length of the study visit will be approximately 4 hours (3 hours pre-scan, 1 hour scan).

Study Visit 2

Location: Sharp and Children's MRI Center ([name])

The morning of the imaging procedures the subject will go to the Sharp and Children's MRI Center for the scanning procedures. The medication will need to be administered 3 hours before the start of the scan.

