The feasibility procedures will also include assessment of side effects from the medication. In case a study participant was to have a serious reaction (such as anaphylaxis) 911 would be called immediately and the person transported to the medical emergency room that is located about 500 yards away on campus. The study personnel are trained in basic life support.

Cardiac conduction abnormalities have been noted in individuals with anorexia nervosa. To ensure patient safety, we will only include patients in our study that are considered medically stable by the Medical Director at UC San Diego Health Eating Disorders Center for Treatment and Research (i.e. normal EKG and lab electrolyte values). If the staff at those facilities does not feel their patient is stable enough to complete the fMRI scan, the study will be postponed until she is stable, or the patient will be withdrawn from the study if timing does not allow the scan to be postponed. Study participants will have their blood pressure and heart rate taken prior to study drug administration as well as at the end of each study day. In case there is a significant drop in blood pressure indicating orthostasis during the study or due to the study medication, we will keep study participants in our research space and provide them with fluids and will recheck the blood pressure until

it has normalized. In case there were ongoing indication of orthostasis we will refer the participant to the local emergency room on campus.

Electrocardiogram. The risk is minimal. Any skin irritation from the electrode placement usually lessens within a few minutes of removing the electrode.

Data and Safety Monitoring Plan

Data will be analyzed as above for brain imaging data. The behavioral data will be analyzed using SPSS statistical software on password protected computers. The PI will perform data analysis with some research assistant support.

Subjects will be continuously monitored during their study participation by asking about how subjects feel and if they have any problems while in the study. However, in case of unexpected effects, the PI will report those to UCSD HRPP.

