25. INVESTIGATIONAL DRUG FACT SHEET AND IND/IDE HOLDER

Drug Names: Bromocriptine mesylate; Amisulpride

IND #: 191908

IND holder: [name]

[name] and the Lab Manager will be responsible for monitoring the study in the following ways:

Medication Handling and Storage

- Per 21CFR §312.6 Labeling of an investigational new drug, medications will be stored in a locked cabinet in the research office of the PI. That office is embedded in the UCSD Eating Disorder Research Program office suite, which is locked. Each study drug will be labeled with the statement “Caution: New Drug—Limited by Federal (or United States) law to investigational use.”
- Per 21CFR §312.61 Control of the investigational drug, the investigator will not supply the investigational drug to any person not authorized under this part to receive it.

Subject Level

- [name] will review all Pre-Scan Blood Test and EKG results to ensure subject's medication risks are minimized.
- Research staff will complete symptom checklist on each Study Visit day and will document the following: Documentation of blood pressure & heart rate pre-medication administration and post scan; symptom checklist including: nausea, headache, dizziness, tiredness, other. Research Staff will report these values to [name] and the Lab Manager at the end of the Study Visit.
- Research staff will contact [name] and/or Lab Manager via phone if there is a significant drop in blood pressure (20 or more points systolic) after the medication administration or significant symptoms that the subject feels keep her from continuing the study.
- [name] or Lab Manager will confirm with research team that all unexpected or adverse events (AEs/SAEs) have been reported to the IRB and FDA in the required timeframe.
- [name] or Lab Manager will review each subject folder after the subject completes the study to ensure required documentation and procedures have been completed.

Study Level

- The Lab Manager will prepare monthly aggregate reports of the adverse events, serious adverse events, and unexpected events and will review with [name].
- [name] will review monthly aggregate reports to determine safety of the study medications and whether the study is safe to be continued.

Per FDA Approval, [name] will be responsible for the following reporting requirements:

- [name] will report any unexpected fatal or life-threatening suspected adverse reactions to FDA no later than 7 calendar days after initial receipt of the information.

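### No blood pressure or heart rate reading is scheduled between the dose and the end of the scan, so a symptom-free fall is not scheduled to be measured before scanner entry

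*Combined protocol and SAP*

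**What the plan says.** Section 9 (Timeline, Study Visits 1 to 3) has the research assistant take blood pressure and heart rate on arrival and then give the study drug. Questionnaires, breakfast, task review and the scan follow. The next reading comes at the end: "After the scan, the research assistant will take the subject's blood pressure and heart rate". The sequence is the same at all three visits and for both recruitment routes. On duration it says: "The total length of the study visit will be approximately 4 hours (3 hours pre-scan, 1 hour scan".

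Two other sections confirm the two times. Section 15 states that participants have their "blood pressure and heart rate taken prior to study drug administration as well as at the end of each study day". Section 25 (Subject Level) lists "Documentation of blood pressure & heart rate pre-medication administration and post scan". The Study Procedures Charts in section 9 have no vital-signs row.

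The scan is timed to the drugs. Section 9 (Special Pharmacological Considerations) says: "Both medications have a plasma peak of 3 hours, and fMRI will begin for all sessions at that time point".

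Two rules respond to a fall in pressure. Section 25 has staff telephone the responsible study lead if systolic pressure drops by 20 points or more after dosing. Section 15 provides fluids, rechecks and, if needed, emergency referral; it begins "In case there is a significant drop in blood pressure indicating orthostasis during the study or due to the study medication".

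Other safeguards are:
- screening of AN patients ("we will only include patients in our study that are considered medically stable by the Medical Director");
- stopping criteria for nausea, dizziness or other interfering symptoms;
- a well-being assessment after dosing, with no method or time given;
- ongoing questions about how participants feel;
- a symptom checklist on each visit day, with no time given.

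**The concern.** The plan sets a numerical trigger and a response, but before the scan no scheduled measurement can set either in motion. The participant enters the scanner at what the plan calls the peak of drug exposure, and her pressure has not been due for measurement since before the dose. A fall that causes complaints should be picked up by the symptom questions. A fall without complaints would be measured beforehand only if someone took an unscheduled reading.

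Two things are at stake. The first is safety: the plan itself anticipates orthostasis and notes cardiac conduction abnormalities in AN, and it lists faintness and fainting for ongoing bromocriptine use. The second is information: tolerability in AN is a stated goal, and "The feasibility procedures will also include assessment of side effects from the medication". As scheduled, the pilot will have no vital-sign value from the three hours between dose and scan.

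**Working it through.** **1. Scheduled times.** Inputs are from section 9, confirmed by sections 15 and 25.

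| Event | Time from dose | Scheduled BP/HR |
|---|---|---|
| Arrival, before dose | just before 0 h | yes |
| Questionnaires, breakfast, task review | 0 to 3 h | none |
| Scan start (stated peak) | 3 h | none |
| After scan | about 4 h | yes |

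Scheduled readings between dose and scanner entry: 0.

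**2. Earliest post-dose value.** The plan's own figure is 3 h + 1 h = about 4 h. Cross-check from the tasks: the taste task takes about 28.5 min and the reversal task 3 × 8.5 = 25.5 min, together 54 min. The earliest post-scan reading is therefore at 3 h 54 min, which agrees with the stated hour.

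**3. What the post-scan reading still shows.** Assume simple decay from a 3 h peak, which ignores amisulpride's earlier peak at 1 h. The fraction of peak left 0.9 h later is 0.5^(0.9 / half-life):
- bromocriptine, 2 h half-life: 0.5^0.45 = 0.73;
- bromocriptine, 8 h: 0.5^0.1125 = 0.92;
- amisulpride, 12 h: 0.5^0.075 = 0.95.

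The late reading is informative about tolerability, but too late to act on before the scan.

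**4. How many visits.** Section 10 plans 44 completers, so there are 44 × 2 = 88 active-drug visits. The AN share of completers is not stated. I assume 20 (section 9, Statistical Power) to 22 (half of 44), giving 20 to 22 AN visits per active drug.

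The documents give no rate for a symptom-free fall. Purely as illustration, assumed rates of 1%, 5% and 10% on AN bromocriptine visits would mean 0.2, 1.0 and 2.0 falls in 20 visits, or 0.22, 1.1 and 2.2 in 22.

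**5. What an added reading would yield.** If no drop were seen in n AN participants on one drug, the one-sided 95% upper bound is 1 − 0.05^(1/n): 13.9% for n = 20 and 12.7% for n = 22. A reading at about 2 h 30 min would give a bound for that time, not for scan start.

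**6. Room in the wait.** Listed pre-scan scales: FCQ-S 5 + HTPS 5 + LMS 2 + PANAS 5 + EEI 5 + BDI-II 5 + EDE-Q 15 + TEPS 5 = 47 min. Counting a post-meal PANAS as well gives 52 min. With an assumed 5 min for the reading this is 57 min, leaving 180 − 57 = 123 min for breakfast, task review and any recheck.

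**The case against.** The strongest reply is that participants are not left unwatched. Staff ask how they feel throughout, a well-being check of unstated content follows dosing, the PI is available during the experiment, and the participant holds an emergency button in the scanner. The section 25 trigger applies at any time after dosing, and nothing bars an unscheduled reading. A promised procedure protocol (section 15) and a Medication Effects Log (section 16) might also set times that these documents do not show. All of this stands. A reader might infer from the schedule that a silent fall could not be detected before the scan; the documents support only that no measurement of it is scheduled.

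A second reply is that orthostasis is a problem of standing. The post-scan reading comes before the participant leaves, near peak drug level, with a response attached. That makes the existing reading useful, and no specific harm from a symptom-free fall inside the scanner is described. It does not give the section 25 rule anything scheduled to act on before the scan.

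Third, the signal differs by drug. Dizziness, faintness and fainting are listed for bromocriptine. Amisulpride's list has a change in heart rate but no faintness or fainting. For a single bromocriptine dose the plan expects at most nausea, headache or dizziness. This keeps the priority modest.

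Fourth, an added reading has side effects of its own. Fluids given before a taste-reward task could alter the state being studied, and a held scan could hint at allocation. Both are fair and are dealt with in the fix.

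**Conclusion.** The point holds as a narrow gap. Every statement on vital signs gives two times only, so there is no scheduled value between the dose and about 4 hours later. Neither the 20-point call nor the recheck steps can be triggered by a scheduled measurement before scanner entry. What is left uncovered is a fall without symptoms that nobody happens to measure.

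The risk is modest and its rate unknown; the counts in the working are multiples of assumed rates, not evidence of size. The AN completer numbers are also assumed.

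Two stronger readings are not supported. One is that the pilot would have no useful post-dose vital signs: the post-scan value falls at roughly 73% to 95% of peak under simple decay. The other is that an added reading would describe scan start: it would describe about 2.5 h after the dose. The priority is that of a cheap, optional safety improvement.

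**What to change.** In section 9 (Study Visits 1 to 3, both recruitment routes), section 15 and section 25:

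- Add one blood pressure, heart rate and symptom-checklist reading about 2 h 30 min after the dose at every visit, placebo included, in the same posture as the pre-dose reading. It should be taken by the non-scanning staff member who gave the drug.
- If systolic pressure is 20 or more points below the pre-dose value, make the existing section 25 call and recheck before scanning. The PI decides whether to scan.
- Record any fluids given before the taste task.
- Give scan staff no reason for a delay, so that they stay blinded.
- Report drops, and delayed or cancelled scans, by drug and group. Label the value as a pre-scan reading at about 2.5 h.

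Taking the reading about 30 min before the scan leaves time for a recheck without moving the 3 h start. It does not cover amisulpride's 1 h peak; whether to add a reading there is for the study physicians.

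Cost: at an assumed 5 min per visit, 44 × 3 = 132 visits × 5 min = 660 min, or 11 staff hours. The person who gave the drug must be available 2.5 h later; section 9 already has the research assistant who gives the drug take the post-scan reading. An occasional scan will be delayed or cancelled. Each cancelled active-drug scan in AN loses one drug-placebo pair: 1/22 = 4.5% to 1/20 = 5% of the pairs for that drug. A small risk remains that a delay hints at allocation.
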